
 • To evaluate target engagement (TE) up to 56 days following a single SC dose of GSK3858279 in healthy participants including cohorts of Japanese, Chinese and Caucasians. 	
 • Reduction (%) from baseline in free CCL17: maximum, minimum and at Days 7, 14, 28 and 56, post-dose • Total CCL17 (free and when bound to GSK3858279): maximum observed concentration (Cmax), time of Cmax (tmax), maximum fold increase compared to baseline, fold increase compared to baseline at Days 7, 14, 28 and 56, post-dose.

 • To assess the potential for anti-drug antibody (ADA) formation 	
 • Incidence of pre-existing ADAs • Incidence of treatment-emergent ADAs over time (and whether neutralising)

 • Exploratory 	
CCI	

Objectives	Endpoints
CCI	

Overall Design:

This is a randomised, double-blind, placebo-controlled, study with a single SC dose of GSK3858279 administered to healthy Caucasian, Chinese and Japanese participants.

To try to eliminate any time dependant variability among ethnic groups, we will aim to treat Caucasian and Asian groups concurrently.

Participants will attend a screening visit at the clinical units within 28 days of Study Day 1. If eligible for the study, participants will return on Day -1 and maybe admitted to the unit overnight for final screening checks in preparation for randomization and dosing (Day 1). Participants will remain at the clinical units until Day 3.

- All participants will remain in the study until at least CCI. It will be mandatory for the Caucasian cohort to continue CCI. The extended follow-up period CCI is to better understand the apparent non complete return of free CCL17 to baseline values as observed in Part A of Study 207804 across all dose groups. CCI (primary endpoints defined from data up to and including Day 57). Safety information will be collected throughout the study.
- Study intervention will be administered as four separate SC injections of either GSK3858279 CCI or placebo in a 7:3 ratio, respectively for each cohort.

Study Population

Although reproductive toxicity studies have not yet been conducted, both males and females (of non-reproductive potential) are permitted under the conditions specified (see Inclusion Criteria).

Healthy participants have been chosen because:

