	
Clinical
 
There were no reports of any clinically significant skin reactions during Part A of the FiH study (207804) in healthy participants.
	
Study Procedures		
Risk associated with blood draws	Fainting, mild pain, bruising, irritation or redness at phlebotomy site, may be associated with blood draws.	Experienced site staff will follow standard approaches for managing events related to blood draws
Other		
SARS-CoV-2	
The current SARS-CoV-2 pandemic can pose a challenge to integrity of the trials, protection of participants' rights, safety and wellbeing and the safety of clinical trial staff. Therefore, risk mitigation strategies will be put in place for this trial and will be evaluated on an ongoing basis for the duration of this trial, or until there is a consensus that the period of the SARS-CoV-2 outbreak in the Australia has passed. If the dynamics of the SARS-CoV-2 outbreak change in such a way that the safety of the trial participants and clinical trial staff or integrity of the data collected during this clinical trial cannot be guaranteed, the trial will be halted.
 
CC1
	
Participant selection and monitoring
 
Healthy subjects in the current study fall in a low risk category for complications of COVID-19, the disease caused by the SARS-CoV-2 virus. To reduce the risk of SARS-CoV-2 infections among trial participants, measures and procedures based on the advice issued by GSK Global COVID Guidance should be followed. These would include but are not limited to counselling participants regarding the importance of infection control measures such as hand washing, reducing inter-personal contacts as much as possible and participant awareness of potential COVID-19 symptoms.

Potential Risk of Clinical Significance	Summary of Data/Rationale for Risk	Mitigation Strategy

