3. OBJECTIVES AND ENDPOINTS

Objectives	Endpoints
Primary	

 To evaluate the safety and tolerability of a single SC dose of GSK3858279 compared with placebo administered to healthy participants including cohorts of Japanese, Chinese and Caucasians 	
 Incidence of adverse events (AEs), serious adverse events (SAEs), withdrawals due to AEs Occurrence of clinically important changes from baseline in clinical laboratory parameters (haematology, clinical chemistry, urinalysis), vital signs (blood pressure, heart rate, body temperature), and cardiac parameters (electrocardiogram)

 To assess the pharmacokinetic (serum PK) profile up to 56 days following a single SC dose of GSK3858279 in healthy participants including cohorts of Japanese, Chinese and Caucasians 	
 PK parameters: area under the concentration-time curve (AUC(0-56), AUC(0-t) post-dose), time of occurrence of last quantifiable concentration (tlast), maximum observed concentration (Cmax), and time of occurrence of Cmax (tmax) per cohort as data permits
Secondary	

 To evaluate target engagement (TE) up to 56 days following a single SC dose of GSK3858279 in healthy participants including cohorts of Japanese, Chinese and Caucasians. 	
 Reduction (%) from baseline in free CCL17: maximum, minimum and at Days 7, 14, 28 and 56, post-dose Total CCL17 (free and when bound to GSK3858279): maximum observed concentration (Cmax), time of Cmax (tmax), maximum fold increase compared to baseline, fold increase compared to baseline at Days 7, 14, 28 and 56, post-dose.

 To assess the potential for anti-drug antibody (ADA) formation 	
 Incidence of pre-existing ADAs Incidence of treatment-emergent ADAs over time (and whether neutralising)
Exploratory	
CCI	

Objectives	Endpoints
CCI	

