
- The QTc is the QT interval corrected for heart rate according to Bazett's formula (QTcB), Fridericia's formula (QTcF), and/or another method, machine-read or manually over-read.
- The specific formula that will be used to determine eligibility and discontinuation for an individual participant should be determined prior to initiation of the study. In other words, several different formulae cannot be used to calculate the QTc for an individual participant and then the lowest QTc value used to include or discontinue the participant from the trial.
- For purposes of data analysis, QTcF, another QT correction formula, or a composite of available values of QTc will be used as specified in the Reporting and Analysis Plan (RAP).

13. History of Stevens Johnson Syndrome
14. Known immunodeficiency
15. Participants with a chronic infection (e.g., osteomyelitis), who have been receiving treatment within three months prior to dosing or individuals with an active infection.
16. Previous or current history of bleeding diathesis, excessive bleeding or coagulation disorders
17. History of significant medical illness in the opinion of the investigator would interfere with the study procedures and / or assessments

PRIOR/CONCOMITANT THERAPY

18. Intended use of over-the-counter or prescription medication including herbal medications within 7 days prior to dosing (or 14 days if the drug is a potential enzyme inducer) or 5 half-lives (whichever is longer) before the start of study intervention until completion of the follow-up visit, unless, in the opinion of the investigator and sponsor, the medication will not interfere with the study.
19. Live vaccine(s) or plans to receive such vaccines within 1 month of screening until final follow-up visit.
20. Treatment with biologic agents (such as monoclonal antibodies including marketed drugs) within 3 months or 5 half-lives (whichever is longer) prior to dosing
21. Treatment with antiplatelet or anticoagulant agents within 7 days of dosing
22. Major surgery (as per investigator's judgement) within 3 months prior to dosing

PRIOR/CONCURRENT CLINICAL STUDY EXPERIENCE

23. Participation in the study would result in loss of blood or blood products in excess of 500 mL within 3 months.

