
24. Exposure to more than 4 new chemical entities within 12 months prior to the first dosing day.
 
25. Current enrolment or past participation in any other clinical study involving an investigational drug intervention within the last 3 months or 5 half-lives (whichever is longer) of signing the ICF

--

DIAGNOSTIC ASSESSMENTS

26. Presence of Hepatitis B surface antigen (HBsAg) at screening.
 
27. Presence of the Hepatitis B core antibody (HBcAb) at screening.
 
28. Positive Hepatitis C antibody test result at screening.
 
NOTE: Participants with positive Hepatitis C antibody due to prior resolved disease can be enrolled, only if a confirmatory negative Hepatitis C RNA test is obtained
 
29. Positive Hepatitis C RNA test result at screening or within 3 months prior to first dose of study intervention
 
NOTE: Test is optional and participants with negative Hepatitis C antibody test are not required to also undergo Hepatitis C RNA testing.
 
30. Abnormal clinically significant echocardiogram at screening, as assessed by the investigator.
 
31. Cardiac troponin or NT-proBNP levels out of normal range at screening.
 
32. Positive pre-study drug/alcohol screen
 
33. Positive human immunodeficiency virus (HIV) antibody test
 
34. Positive coronavirus (COVID-19): SARS-CoV2 PCR or lateral flow test of a combined throat and nasopharyngeal swab or nasal swab only

OTHER EXCLUSIONS

35. Regular alcohol consumption within 6 months prior to the study defined as:
 
 • an average weekly intake of >11 standard drinks for males and females. One standard drink contains 10g of alcohol. 
36. Regular use of known drugs of abuse.
 
37. Sensitivity to any of the study interventions, or components thereof, or drug or other allergy that, in the opinion of the investigator or medical monitor, contraindicates participation in the study.

--

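### Section 5.2 does not exclude previous recipients of GSK3858279, and the washout it applies is not shown to restore the CCL17 baseline or to keep earlier ADA out of the pre-existing count

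*Protocol*

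**What the plan says.** **Eligibility (protocol section 5.2).**

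- Criterion 25 excludes participation in another investigational-drug study "within the last 3 months or 5 half-lives (whichever is longer) of signing the ICF". The interval runs from past participation to consent.
- Criterion 20 excludes "Treatment with biologic agents (such as monoclonal antibodies including marketed drugs) within 3 months or 5 half-lives (whichever is longer) prior to dosing".
- Criterion 24 excludes "Exposure to more than 4 new chemical entities within 12 months prior to the first dosing day". One earlier course of this antibody would not reach that limit.
- Criterion 37 names the study interventions, but only for "Sensitivity to any of the study interventions, or components thereof". Criteria 6 and 7 likewise concern allergy and hypersensitivity.

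No criterion mentions previous receipt of GSK3858279 or participation in Study 207804.

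**Persistence of the effect (protocol section 1.1).** The extended follow-up is there to understand "the apparent non complete return of free CCL17 to baseline values as observed in Part A of Study 207804 across all dose groups". The text gives neither the size nor the duration. Section 2.3.1 confirms the Part A population: it refers to skin findings "during Part A of the FiH study (207804) in healthy participants".

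**Endpoints.** Secondary endpoints in protocol section 3 include percentage reduction from baseline in free CCL17, fold increase from baseline in total CCL17, and "Incidence of pre-existing ADAs". SAP section 4.1.2 takes the CCL17 baseline as the mean of the Day -2 and Day 1 pre-dose values. SAP section 4.3 has no rule for previously exposed participants, and section 4.3.3 plans no sensitivity analysis.

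**The concern.** Part A of Study 207804 dosed healthy volunteers, the kind of person recruited here. Under section 5.2 as written, one of them who is past the washout is eligible.

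A washout in half-lives deals with clearance of the drug. The target-engagement endpoints need something else: a CCL17 level that has returned to its natural value. The protocol itself doubts that this had happened in Part A. Averaging two baseline samples taken within a few days of each other does not help, because both would carry the same residual effect.

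Three secondary summaries are exposed. A free CCL17 baseline that is still suppressed makes the percentage reduction look smaller. A total CCL17 baseline that is still raised makes the fold increase look smaller. ADA raised by an earlier dose and found in the pre-dose sample would be counted as pre-existing. With about 7 active participants per cohort and a study meant to compare ethnic groups, one such person in one cohort could add a small artificial difference.

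**Working it through.** The plan states no figure on this point. The check is a reading of the criteria followed by arithmetic on assumed carry-over.

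**1. What the washout achieves.** Under first-order elimination, the drug remaining after 5 half-lives is 2^-5 = 3.1%. The half-life is not readable in the documents. Taking 3 months as about 91 days, the longer of 3 months and 5 half-lives would be:

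| Assumed half-life | 5 half-lives | Washout applied |
|---|---|---|
| 14 days | 70 days | 91 days |
| 21 days | 105 days | 105 days |
| 28 days | 140 days | 140 days |

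None of these intervals is tied to recovery of CCL17.

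**2. Effect on one person's free CCL17 reduction.** Let r be the true reduction from the natural level and q the residual suppression at entry. The post-dose level is taken as (1 - r) of the natural level whatever the baseline.

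Apparent reduction = 1 - (1 - r)/(1 - q). The range 10% to 30% for q is an assumption.

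- r = 50%: q = 10% gives 1 - 0.5/0.9 = 44.4%; q = 30% gives 1 - 0.5/0.7 = 28.6%.
- r = 80%: q = 10% gives 1 - 0.2/0.9 = 77.8%; q = 30% gives 1 - 0.2/0.7 = 71.4%.

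**3. Effect on the cohort.** The endpoints are summarised by cohort, with 7 randomised to active (protocol section 9.3). With one affected participant of 7, the arithmetic mean becomes:

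- True 50%: (6 × 50 + 44.4)/7 = 49.2%; (6 × 50 + 28.6)/7 = 46.9%.
- True 80%: (6 × 80 + 77.8)/7 = 79.7%; (6 × 80 + 71.4)/7 = 78.8%.

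The shift is about 0.3 to 3 percentage points.

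**4. Total CCL17 fold increase.** If one person's baseline is raised by a factor b, that person's fold increase is divided by b. The geometric mean of 7 is multiplied by b^(-1/7). For an assumed b of 1.1 this is 0.986 (1.4% lower); for b = 2 it is 0.906 (9.4% lower).

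**5. Pre-existing ADA.** One carried-over positive adds 1/10 = 10 percentage points in a cohort of 10, or 1/7 = 14.3 points among the active participants.

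**The case against.** The strongest reply is that nobody at risk has been shown to exist. The sites of Study 207804 are not given. Its Part B enrolled people with knee osteoarthritis, most of whom would fail the requirement to be overtly healthy. The Part A interim report is dated 7 September 2020, 16 months before Amendment 1 of this protocol (11 January 2022), so the doses it covers were well in the past. Criterion 25 also counts from participation, so Part A follow-up may lengthen the gap since dosing. This stands as an argument about likelihood: such entrants are probably few. The documents do not say whether Part A dosing continued later.

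A second reply is that the observation in Part A is hedged and unquantified. If Part A followed people for less than 5 half-lives, incomplete return there says nothing against a 5-half-life washout. This also stands. A reader might infer that free CCL17 definitely failed to recover, or that the washout is too short. The documents support neither, only that its sufficiency for CCL17 is not shown.

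A third reply is that carry-over would be visible: medication history is taken at screening, and PK, target-engagement and ADA samples are taken before dosing. That would help to find an exposed participant. It does not exclude one, and neither document says how to analyse one.

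A fourth reply is that Study 207804 was double-blind, so a screening site may not know who had placebo. That does not defeat the remedy if unknown allocation leads to exclusion.

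**Conclusion.** The gap is real and of low severity. Section 5.2 admits a previously dosed healthy volunteer after the longer of 3 months and 5 half-lives. Neither document shows that this restores the CCL17 baseline, and neither separates ADA from an earlier dose from naturally pre-existing ADA.

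The effect falls on secondary endpoints that are summarised descriptively, with no hypothesis tested. On the free CCL17 endpoint it is about 0.3 to 3 points on a cohort mean. That assumes one affected person among 7 active, 10% to 30% residual suppression, and a post-dose level that does not depend on the earlier dose. The residual suppression has no source in the documents. The pre-existing-ADA count is the most sensitive, because one case is 10 points in a cohort of 10.

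Three stronger readings should be resisted:

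- The single-person distortion (50% read as 29%) is not the error in the reported cohort result.
- The primary safety and PK objectives are not shown to be biased.
- A reader might infer that re-exposure raises the hypersensitivity risk. The readable text of section 2.3.1 links that risk to giving any monoclonal antibody and to ADA formation, and says nothing about re-exposure, so no safety argument is made here.

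**What to change.** Add one criterion to section 5.2, for example: *Any previous exposure to GSK3858279, including participation in Study 207804 unless allocation to placebo is documented (if allocation is unknown, exclude).* Leave criteria 20 and 25 as they are for other products.

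If enrolment has closed, identify any previously exposed participants from the medication and study history. State in the SAP that the target-engagement and pre-existing-ADA summaries will be repeated without them, and report the number found even if it is zero.

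The cost is one exclusion line, one screening question and a negligible loss of recruitment pool. Some former placebo recipients whose allocation cannot be documented would be turned away.

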5.3. Lifestyle Considerations

5.3.1. COVID-19 related restrictions

Participants will be required to adhere to the measures and procedures outlined in the hospital policy, based on the advice issued by the State health minister and COVID-19 measures declared by the Australian government, to reduce risk of SARS-CoV-2 infections among trial participants and clinical site staff.

5.3.2. Meals and Dietary Restrictions

Not Applicable.

5.3.3. Caffeine, Alcohol, and Tobacco

- Participants will not be allowed to have excessive caffeine consumption, defined as >800 mg per day from 7 days prior to the first dose of the study drug until 24 hours prior to dosing. Participants will abstain from caffeine-containing products for 24 hours prior to each visit to the study unit. Caffeine quantities defined as: one cup of coffee contains 100 mg of caffeine; one cup of tea, or one glass of cola, or portion of chocolate (dark: 100 g, milk: 200 g) contains approximately 40 mg of caffeine; one 250 ml can of Red Bull contains approximately 80 mg of caffeine.
- Alcohol will not be allowed from at least 24 hours before each scheduled visit, and whilst in the study unit until discharge from the study unit. At other times throughout the study, participants should not consume more 1.5 standard drinks of alcohol daily on average (10g alcohol in 1 Australian standard drink). Participants may undergo an alcohol breath test at the discretion of the investigator.
- Non-smokers or light smokers (<= 5 cigarettes / nicotine-forms per week) may be enrolled in the trial. Light smokers must abstain from nicotine-containing products for at least 3 days prior to Day 1 dosing and for the duration of the inpatient stay.

5.3.4. Activity

- Participants will abstain from strenuous exercise for 48 hours before each blood collection for clinical laboratory tests. Participants may participate in light recreational activities during studies (e.g., watching television, reading).

5.4. Screen Failures

A screen failure occurs when a participant who consents to participate in the clinical study is not subsequently randomized/entered in the study. A minimal set of screen failure information is required to ensure transparent reporting of screen failure participants to meet the Consolidated Standards of Reporting Trials (CONSORT) publishing requirements and to respond to queries from regulatory authorities. Minimal information includes demography, screen failure details, eligibility criteria, any protocol deviations and any serious adverse events (SAEs).

Repeat assessments during the screening period: Assessments, including laboratory assessments, may be repeated once if determined necessary by the investigator, for example: (a) in cases of technical malfunction (e.g. loss of laboratory specimen), (b) in the event of a value close enough to the exclusionary threshold that it may reasonably lie within the degree of variability of the assay or an indeterminate result; (c) if there is reason to believe the result may be false (i.e. contradicts recent result for the same parameter). These are repeat assessments and not rescreening events. If the original result was exclusionary and is confirmed by repeat testing, the participant will be excluded

Individuals who do not meet the criteria for participation in this study (screen failure) may be rescreened once, unless a positive SARS-CoV-2 test results is obtained where rescreening is not permitted. Rescreened participants should be assigned a new participant number.

6. STUDY INTERVENTION

Study intervention is defined as any investigational intervention(s), marketed product(s), placebo, or medical device(s) intended to be administered to a study participant according to the study protocol.

6.1. Study Intervention(s) Administered

Study intervention is defined as any investigational intervention(s), marketed product(s), placebo, or medical device(s) intended to be administered to a study participant according to the study protocol

Table 1 Study Interventions Administered

ARM Name	Active	Placebo
Intervention Name	GSK3858279	Placebo
Type	CCI [REDACTED]	Placebo
Dose Formulation	CCI [REDACTED] [REDACTED]	Solution for injection. CCI [REDACTED] [REDACTED]
Unit Dose Strength	CCI [REDACTED] [REDACTED] [REDACTED]	CCI [REDACTED] [REDACTED]
Dosage Levels	CCI [REDACTED]	Single dose
Route of Administration	SC injection	SC injection
Dosing Instructions	CCI [REDACTED]	
Use	Experimental	Placebo-control
IMP and NIMP	IMP	Placebo
Sourcing	Study medication is supplied by GSK.	Provided locally by the trial site, subsidiary, or designee.

Packaging and Labelling	Bulk supplies will be provided in a vial contained within a carton. Each vial and carton will be labelled as required per country requirement. Dispensed medication will be labelled as required per country requirement.	Commercial presentation. Dispensed placebo will be labelled as required per country requirement.
--------------------------------	---	--

CC1
 [REDACTED]
 [REDACTED]
 [REDACTED]
 [REDACTED]
 [REDACTED].

6.2. Preparation, Handling, Storage and Accountability

- CC1
 [REDACTED]
 [REDACTED]
 [REDACTED]
 [REDACTED]
- The investigator or designee must confirm appropriate temperature conditions have been maintained during transit for all study intervention received and any discrepancies are reported and resolved before use of the study intervention.
- Only participants enrolled in the study may receive study intervention and only authorized site staff may supply or administer study intervention. All study interventions must be stored in a secure, environmentally controlled, and monitored (manual or automated) area in accordance with the labeled storage conditions with access limited to the investigator and authorized site staff.
- The investigator, institution, or the head of the medical institution (where applicable) is responsible for study intervention accountability, reconciliation, and record maintenance (i.e., receipt, reconciliation, and final disposition records).
- Further guidance and information for the final disposition of unused study intervention are provided in the SRM.
- Under normal conditions of handling and administration, study intervention is not expected to pose significant safety risks to site staff. Take adequate precautions to avoid direct eye or skin contact and the generation of aerosols or mists. In the case of unintentional occupational exposure notify the monitor, Medical Monitor and/or GSK study contact.
- A Material Safety Data Sheet (MSDS)/equivalent document describing occupational hazards and recommended handling precautions either will be provided to the investigator, where this is required by local laws, or is available upon request from GSK.

Precaution will be taken to avoid direct contact with the study intervention. A Material Safety Data Sheet (MSDS) describing occupational hazards and recommended handling precautions will be provided to the investigator. In the case of unintentional occupational exposure notify the monitor, Medical Monitor and/or GSK study contact.

